6.3.2 Treatment compliance

Compliance is defined as $100 * \text{number of tablets taken} / \text{number of tablets planned in actual treatment days}$.

The compliance will be summarized descriptively by treatment group and overall. In addition, compliance will be categorized into three groups (<80%, 80-120%, >120%) and summarized by treatment group and overall.

6.3.3 Safety variables

Safety and tolerability variables are:

- Adverse events (Section 6.3.4), including
 - SAEs, AEs, treatment-emergent AEs and AEs of special interest, including AV blocks $> 1^\circ$
 - SAEs and AEs leading to discontinuation or interruption of study drug, including AV blocks in particular

Statistical Analysis Plan

- Laboratory abnormalities (Section 6.3.6), measured values and change from baseline, in particular
 - Change in renal function measured by eGFR change from baseline
 - Change in liver function measured by bilirubin (total and fractions), AST and ALT from baseline
- 12-ECG abnormalities (Section 6.3.8) and PR interval duration
- Blood pressure and heart rate (Section 6.3.8); measured values and change from baseline
- Number of clinically significant findings in ECG and / or AVIVO / HealthPatch device report

6.3.4 Adverse events

All adverse events (AEs) will be coded according to the Medical Dictionary for Regulatory Activities (MedDRA) in its latest version which is specified in the TS domain.

A treatment-emergent AE is defined as any event arising or worsening after the start of study drug administration until 6 weeks after the last study medication intake.

Summary statistics (frequency and percentage of subjects) will be presented by treatment group using MedDRA for the following:

- Incidence rate of treatment-emergent AEs.
- Incidence rate of drug-related treatment-emergent AEs.
- Incidence rate of treatment-emergent AEs leading to death.
- Incidence rate of treatment-emergent AEs leading to permanent withdrawal of medication.
- Incidence rate of treatment-emergent AEs leading to interruption of medication.
- Incidence rate of treatment-emergent serious adverse events (SAEs).
- Incidence rate of treatment-emergent drug-related SAEs.
- Incidence rate of adverse events of special interest:
 - Symptomatic bradycardia (HR < 50 bpm)
 - Findings in ECG and / or AVIVO device as follows:
 - Mobitz type I AV block leading to withdrawal or interruption of study drug
 - Mobitz type II AV block leading to withdrawal or interruption of study drug or leading to any change in therapy
 - Third degree AV blocks

Statistical Analysis Plan

Listing of treatment-emergent AEs leading to withdrawal: subject ID, investigator AE term, primary SOC / preferred term, start and stop date of study drug administration, start and stop date (relative days) of AE, treatment arm, related to study drug / protocol-required procedure (yes/no), serious (yes/no), intensity, outcome.

Listing of treatment-emergent SAEs: subject ID, investigator AE term, primary SOC / preferred term, worst grade, start and stop dates of study treatment, start and stop date of AE , treatment arm, drug related (yes/no), intensity, outcome, action taken.

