5.1 Design overview

Study 17582 is a multicenter, randomized, placebo-controlled, parallel group, double blind, dose-finding Phase II study. Figure 5—1 displays the overall study design.

Run-in Treatment Follow up placebo Eligibility check, baseline assessments, randomization events / hospitalizations 5 mg eligibility check 10 mg of treatment Safety follow-up 20 mg 30 mg End 40 mg W 4 W 8 W 12 W 20 W 26 W2 W 19 W 0 W 24 W -1 Visit 3, Visit 4 Visit 5 Visit 6 Phone call Visit 7 Visit 9 Visit 2 Visit 8 Visit 1 phone call phone call

Figure 5—1: Study design overview

Abbreviations: CV = cardiovascular; ICF = informed consent form; W = week

Approximately 288 patients from approximately 90 study centers worldwide will be randomized to one of the active treatment dose arms or placebo, in addition to their background therapy (for details see Section 7).

The study will comprise a 1-week run-in period, 20-week treatment period, and a 6-week follow-up period (27 weeks total).

Patients will have site visits at Weeks -1, 0 (baseline), 4, 8, 12, 20 (end of treatment visit) and 24 (safety follow-up visit). In addition, 2 phone calls at Weeks 2 and 26 will be made to assess patients' safety, and one additional phone call – to remind the patients of AVIVO self-application at Week 19.

6MWD test (including Borg CR 10 Scale) will be done during the run-in, to familiarize patients with the test, and at baseline, Week 8 and end of treatment / premature discontinuation visits. Safety will be monitored throughout the study. PK samples will be taken from all patients at dedicated time points. Biomarkers reflecting the pharmacodynamic activity of the drug will be examined, as well as candidate biomarkers that may predict drug response.

For detailed visit descriptions and rules for patients who discontinue study treatment earlier, please see Sections 9.1 and 9.2.

The anticipated duration of the study as a whole is approximately 19 months: this includes an anticipated recruitment period of 13 months followed by a run-in period of 1 week, a treatment period of 20 weeks and a follow-up period of 6 weeks after enrollment of the last patient into the trial.

14 FEB 2017 Version: 1.0 Page: 23 of 85

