 (e.g. social hospitalization for purposes of respite care).

However, it should be noted that invasive treatment during any hospitalization may fulfill the criterion of 'medically important' and as such may be reportable as an SAE dependent on clinical judgment. In addition, where local regulatory authorities specifically require a more stringent definition, the local regulation takes precedence.

- d. Results in persistent or significant disability / incapacity
 Disability means a substantial disruption of a person's ability to conduct normal life's functions.
- e. Is a congenital anomaly / birth defect
- f. Is another serious or important medical event as judged by the investigator

Definition of treatment-emergent adverse event

An AE is classified as treatment-emergent if it occurs or worsens after the first dose of study drug up to 6 weeks after the last dose of study drug.

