9.6.1.3 Assessments and documentation of adverse events

The investigator has to record on the respective CRF pages all adverse events occurring in the period between the signing of the informed consent and the end of the follow-up phase (Visit 9); after the end of the follow-up phase there is no requirement to actively collect AEs including deaths. The type of information that should be assessed and recorded by the investigator for each AE is listed in Section 9.6.1.2.

"Death" should not be recorded as an AE on the AE page. Instead, "death" is the outcome of an underlying AE(s).

For all serious adverse events (SAEs) the sponsor has to carry out a separate assessment for expectedness, seriousness and causal relationship to study drug.

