These numbers already include adequate assumptions on expected drop-out after randomization and invalid or missing data. In the selected population it is expected that only about 75% of all randomized patients, i.e. about 216 patients, will contribute complete data to the primary analysis in the PPS.

All power estimations and simulations were performed with the DoseFinding package in R, version 3.2.3 (2015-12-10).

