4.3 Handling of Missing Data

Generally, missing data will be handled as such, i.e., no imputation of missing data will be performed. An exception is the analysis of the primary and secondary efficacy variables, and the timing of events relative to other events.

All missing or partial data will be presented in the patient data listing as they are recorded in the eCRF.

A number of descriptive analyses will be performed to better understand missing data patterns. The frequency, proportion and the reasons for premature discontinuation of both the study and study treatment will be reported. Kaplan-Meier plots for “time to end of study treatment (calculated as days from first dose to the earliest date of stop medication, including premature stop of study medication and death, for the calculation all the subjects will be considered to have an event, i.e. stop of study medication)” and “time to end of study” (calculated from randomization to the earliest date of visit 9, death, and the last visit if subject drops off from study prematurely, for the calculation all the subjects will be considered to have an event, i.e. stop of study) will be provided, by treatment group and overall.

The number of patients who prematurely discontinue study participation or intake of study medication and the corresponding reasons will be summarized with respect to the key subgroups (see Section 4.5.4). If the proportion of patients who withdraw across the dose groups is not fairly balanced, the impact on the primary variables will be further explored. To further explore the missingness pattern with regards to the “missing at random” assumption, the mean of the baseline values of the efficacy variable will be summarized for patients with and without post-baseline observations, by treatment group and overall.

For the analysis of the primary and secondary variables, it cannot necessarily be assumed that data are missing at random. As the choice of primary analysis will be based on assumptions that cannot be verified, the robustness of the results of the primary analysis will be investigated through appropriate sensitivity analyses making different assumptions, in accordance with the EMA “Guideline on missing data in confirmatory clinical trials”. Detail missing data handling are specified in Section 6.2.1.4.

When appropriate, the following rules will be implemented so as not to exclude subjects from statistical analyses due to missing or incomplete data:

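### Adverse event percentages in SAP 6.3.4 are not adjusted for time at risk, so they can run modestly low in arms with more early stopping, for events that are unrelated to stopping and occur at a steady or late rate

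*SAP*

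**What the plan says.** **Measure.** SAP 6.3.4 introduces its adverse event tables with "Summary statistics (frequency and percentage of subjects) will be presented by treatment group using MedDRA for the following" and then names each of the eight rows an incidence rate. Protocol 10.3.2.4 makes the adverse event tabulations descriptive only, and SAP 6.3 rules out formal tests. Neither document plans a person-time rate or a cumulative incidence for adverse events.

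**Window.** SAP 6.3.4 counts as treatment-emergent "any event arising or worsening after the start of study drug administration until 6 weeks after the last study medication intake". Protocol 9.6.1.1 agrees: an event is "treatment-emergent if it occurs or worsens after the first dose of study drug up to 6 weeks after the last dose of study drug". Seven of the eight rows carry the treatment-emergent label. The row for adverse events of special interest does not, and no window is given for it.

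**Collection.** Protocol 9.6.1.3 requires adverse events to be recorded from consent to Visit 9 (Week 26). Protocol 9.2.10 keeps the Week 26 call for patients who stop treatment early. Later events in early stoppers are therefore collected, but they fall outside the treatment-emergent tables.

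**What is shown about stopping.** SAP 6.3.1 summarises treatment duration by arm. SAP 4.3 plots time to end of treatment and adds: "If the proportion of patients who withdraw across the dose groups is not fairly balanced, the impact on the primary variables will be further explored". That further look concerns efficacy, not the adverse event tables.

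**The concern.** A percentage of subjects compares arms fairly only if patients are observed for similar lengths of time. Here the countable time depends on when each patient stops. If stopping rises with dose, the higher-dose arms have less time in which an unrelated event can be counted, and a true dose relation for such events could be flattened.

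This matters because SAP 6.2.1.2 (Step 2) makes the final choice of target dose depend partly on safety, and untested descriptive tables will inform that choice. Uneven stopping is possible in this design: Protocol 7.1 allows no dose modification, so a patient who does not tolerate the assigned dose can only interrupt or stop. The SAP already uses time-to-event displays for adjudicated outcomes (6.2.3), but nothing comparable for adverse events.

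**Working it through.** **The plan's own figures.** There is no adverse event rate, stopping rate by arm or safety precision to reproduce. The time frame does reproduce: 1 + 20 + 6 = 27 weeks in total (Protocol 5.1), of which 20 + 6 = 26 follow the first dose.

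**Time at risk.** A patient who stops at week t has t + 6 weeks in the window: 10 weeks for t = 4 and 14 for t = 8, against 26 for a completer.

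**Main illustration (assumed rates).** Constant hazard, the same in every arm, with a 26-week risk of 20%. A share s stops at week t, for reasons unrelated to the event.

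- Hazard per week: λ = −ln(1 − 0.20)/26 = 0.00858.
- Risk within the window: F(u) = 1 − exp(−λu), so F(10) = 8.2%, F(14) = 11.3%, F(26) = 20%.
- Expected crude percentage: (1 − s) × 20% + s × F(t + 6).

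| Share stopping | Stop at Week 4 | Ratio to 10% | Stop at Week 8 | Ratio to 10% |
|---|---|---|---|---|
| 10% | 18.8% | – | 19.1% | – |
| 25% | 17.1% | 0.91 | 17.8% | 0.93 |
| 35% | 15.9% | 0.84 | 17.0% | 0.89 |

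For stopping at Week 4, the gaps from the 10% arm are about 1.8 and 2.9 percentage points. In a 48-patient arm (Protocol 10.4) that is about 0.8 and 1.4 patients. The binomial standard error of a 20% proportion with n = 48 is √(0.20 × 0.80/48) = 5.8 points, so the gap is well inside sampling noise for one arm. It is a systematic shift, though, and would apply to every event type of this kind.

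First events per patient-week at risk would equal λ, about 0.86 per 100 patient-weeks, in every arm whatever its stopping share.

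**Wider range (assumed rates).** With a 30% risk, stopping at Week 4, and 10% against 25% stopping, the crude figures are 28.3% and 25.7%. Two arms showing equal percentages would then conceal a hazard ratio of about 1.12. Over 26-week risks of 10 to 60%, stopping at Weeks 2 to 8, and 10% against 25% or 40% stopping, the gap runs from 0.7 to 10.7 points and the concealed hazard ratio from 1.08 to 1.40. The upper ends need frequent events and very uneven, very early stopping.

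**Where the effect shrinks or reverses.**

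- Early events: put 70% of the cumulative hazard in the first 4 weeks and keep the 30% risk and Week 4 stopping. The figures become 29.4% and 28.6% at 10% and 25% stopping, a gap of 0.8 points instead of 2.6.
- Events that cause stopping: these are counted. If every stopper stops because of the event and the others have a 30% risk, the percentage is s + (1 − s) × 0.30, which is 37.0% at 10% stopping and 47.5% at 25%. The arm with more stopping looks worse.

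**The case against.** The case for leaving the plan alone is substantial, and most of it stands.

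- **Direction.** A reader might infer that arms with more early stopping will look safer. The documents do not support that as a general statement. An event that leads to withdrawal is inside the window, and SAP 6.3.4 gives such events their own row. The downward shift is confined to other events with a steady or late rate.
- **Serious outcomes.** SAP 6.3.5 tabulates deaths later than 6 weeks after last dose as well. SAP 6.2.3 gives Kaplan-Meier estimates for adjudicated cardiovascular death, heart failure hospitalization and urgent heart failure visits, to Week 26 and on treatment, by arm and pooled dose. These are largely protected.
- **Events of special interest.** It is tempting to say they are cut off at 6 weeks too. Their row is not labelled treatment-emergent, so the window is unstated, not short. The Mobitz I and II items are also defined partly by withdrawal or interruption, so stopping helps to create those cases.
- **Stopping rates.** It is also tempting to read "only about 75% of all randomized patients, i.e. about 216 patients, will contribute complete data" (Protocol 10.4) as an expected 25% stopping rate. It is not one: it describes evaluability for the primary analysis, covers invalid and missing data as well as drop-out, and is not split by arm. The SAP 4.3 sentence on imbalance is conditional and predicts nothing.
- **Visibility.** Exposure summaries and the plot of time to end of treatment would show an imbalance. They would not adjust any adverse event figure.
- **Definition.** A window that ends 6 weeks after last dose is a deliberate choice, and Protocol and SAP agree on it. The label incidence rate is explained in the line above the list, so that fault is one of wording.

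What remains is that no planned adverse event table takes account of time at risk, and that events collected after the window appear in no comparative table other than those for deaths and adjudicated outcomes.

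**Conclusion.** The point holds as a minor, conditional one. If early stopping differs between doses, the crude percentages in SAP 6.3.4 can be modestly too low in the arms with more stopping, for events that are unrelated to stopping and occur at a steady or late rate. Under the main assumptions (20% risk over 26 weeks, constant and equal hazards, stopping at Week 4, 10% against 25 to 35% stopping) the shift is about 2 to 3 percentage points, or roughly one patient per 48-patient arm. All event and stopping rates here are assumptions. If stopping turns out even across arms, the differential shift disappears. Nothing here questions the treatment-emergent definition or suggests that the safety tables would be misleading overall. The change is worth making because it is cheap and these tables feed the dose choice.

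**What to change.** In SAP 6.3.4:

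1. Keep the percentages, and call them percentages of subjects.
2. For treatment-emergent adverse events and serious adverse events, add by arm the patient-weeks at risk (first dose to first event, or to the earlier of last dose + 6 weeks and end of follow-up) and first events per 100 patient-weeks.
3. Add one table of all adverse events and serious adverse events from first dose to Week 26 regardless of last dose. The rate in item 2 still stops at the window, so only this table brings in the later events.
4. State the counting window for adverse events of special interest.
5. Optionally, add cumulative incidence of serious adverse events by arm and for the pooled dose groups of SAP 6.2.3.

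**Cost.** SAP wording, extra columns and one extra table. Collection to Visit 9 is already planned, and Kaplan-Meier methods are already in the SAP.

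**Limits to state with the tables.**

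- The rate assumes a roughly constant hazard.
- Censoring at last dose + 6 weeks assumes that stopping is non-informative, which is doubtful if patients stop for tolerability.
- Person-time is a poor denominator for ECG and AVIVO findings, which are detected at scheduled recordings (Protocol Table 9—1) and not continuously.
- In early stoppers, events after the safety visit (4 weeks after last dose) rest mainly on the Week 26 call, so the table in item 3 may under-record them.

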6.3.5 Deaths

Deaths reported during the study period will be tabulated by treatment group.

- Summary table of deaths (all deaths, all deaths during treatment and up to 6 weeks after last dose of study drug, all deaths later than 6 weeks after last dose of study medication)
- Listing of subjects who died during treatment and up to 6 weeks after last dose: subject ID, start and stop date of study medication, date of death, and cause of death.

6.3.6 Clinical laboratory evaluations

All laboratory evaluations will be done by central laboratory.

Hematology: erythrocytes, hemoglobin, hematocrit, MCV, MCH, MCHC, reticulocytes, leukocytes, differential blood count, platelets

Clinical chemistry: aspartate aminotransferase (AST), alanine aminotransferase (ALT), alkaline phosphatase (AP), gamma glutamyl transpeptidase (GGT), lactate dehydrogenase (LDH), creatine kinase (CK), amylase, lipase, glucose, cholesterol (HDL, LDL, total), triglycerides, creatinine, urea, uric acid, bilirubin, total protein, albumin, sodium, potassium, calcium, chloride, magnesium, anorganic phosphate

Coagulation: partial thromboplastin time (PTT), international normalized ratio (INR)

The safety evaluation of laboratory data will include:

- Descriptive analysis of continuous laboratory parameters, and their changes from baseline by visit and treatment group.
- Incidence rates of treatment-emergent laboratory values outside of normal range by treatment group.
- Listings of laboratory data out of normal range.

Laboratory abnormalities will be summarized in table of change from baseline by visit and treatment:

- Change in renal function measured by eGFR from baseline
- Change in liver function measured by bilirubin (total and fractions), AST and ALT from baseline

Statistical Analysis Plan

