9.6.3 Further safety

9.6.3.1 Laboratory evaluations

All laboratory evaluations will be done by central laboratory. Additional re-tests for liver monitoring (Section 9.6.3.6) will be done locally.

Hematology: erythrocytes, hemoglobin, hematocrit, MCV, MCH, MCHC, reticulocytes, leukocytes, differential blood count, platelets

Clinical chemistry: aspartate aminotransferase (AST), alanine aminotransferase (ALT), alkaline phosphatase (AP), gamma glutamyl transpeptidase (GGT), lactate dehydrogenase (LDH), creatine kinase (CK), amylase, lipase, glucose, cholesterol (HDL, LDL, total), triglycerides, creatinine, urea, uric acid, bilirubin, total protein, albumin, sodium, potassium, calcium, chloride, magnesium, anorganic phosphate

Coagulation: partial thromboplastin time (PTT), international normalized ratio (INR)

14 FEB 2017 Version: 1.0 Page: 54 of 85

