9.6.3.6 Liver function monitoring

Any patient with an ALT or AST > 3 x ULN or alkaline phosphatase (AP) > 2 x ULN must be re-tested as soon as possible but at the latest within 48-72 hours of the investigator becoming aware of the result. This re-testing and any subsequent testing based on elevated levels should include measurement of ALT, AST, total and direct bilirubin, and AP, and will be assessed by local laboratory. Every effort should be made to clarify the etiology of elevated levels. Patient management is at the discretion of the investigator but the treating physician may continue the study drug during retesting. Liver function test monitoring should be performed as above for all patients even if the study drug is interrupted until tested values have normalized or returned to patient's baseline. If close liver monitoring is not possible then the patient should discontinue study medication.

For ALT or AST > 3 x ULN concurrent with a total bilirubin > 2 x ULN, every effort should be made to clarify any possible underlying disease(s).

The frequency of liver function tests based on re-test values is shown in Table 9—3.

Table 9—3: Liver function monitoring

ALT, AST or AP level at re-test	Frequency	Further notice
ALT or AST > 3 x ULN	2-3 times a week	Obtain details on liver related symptoms and exclude other causes of liver enzyme elevations
ALT or AST ≤ 3 x ULN	Once a week	Until return to normal or patient baseline levels
AP > 2 x ULN	2-3 times a week	Obtain details on liver related symptoms and exclude other causes of liver enzyme elevations

ALT = alanine aminotransferase; AP = alkaline phosphatase; AST = aspartate aminotransferase; ULN = upper limit of normal

Discontinuation of treatment should be considered if:

- ALT or AST > 8 x ULN
- ALT or AST > 5 x ULN for more than 2 weeks
- ALT or AST > 3 x ULN and (total bilirubin > 2 x ULN or INR > 1.5)
- ALT or AST > 3 x ULN with the appearance of fatigue, nausea, vomiting, right upper quadrant pain or tenderness, fever, rash, and / or eosinophilia (> 5%)
- AP > 2 x ULN or ALT/AP < 2 for more than 2 weeks if other causes of cholestasis are excluded

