10.3.1.4 Safety variables

Safety and tolerability variables are:

- Adverse events (Section 9.6.1), including
 - SAEs, AEs, treatment-emergent AEs and AEs of special interest, including AV blocks > I°
 - SAEs and AEs leading to discontinuation of interruption of study drug, including AV blocks in particular
- Laboratory abnormalities (Section 9.6.3.1), measured values and change from baseline, in particular
 - o Change in renal function measured by eGFR change from baseline
 - Change in liver function measured by bilirubin (total and fractions), AST and ALT from baseline
- 12-ECG abnormalities (Section 9.6.3.3) and PR interval duration
- Blood pressure and heart rate (Section 9.6.3.4); measured values and change from baseline
- Number of clinically significant findings in ECG and / or AVIVO device report

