4.1 General Principles

The statistical evaluation will be performed by using the software package SAS version 9.2 or higher (SAS Institute Inc., Cary, NC, USA). Unless otherwise noted, data will be analyzed by descriptive statistical methods: The number of data available and missing data, mean, standard deviation, minimum, quartiles, median, and maximum will be calculated for metric data. Frequency tables will be generated for categorical data.

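### SAP 6.3.6 specifies no count by treatment group of patients meeting the liver criteria of Protocol 9.6.3.6; its only categorical liver summary is cut at the normal range

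*SAP*

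**What the plan says.** Protocol 9.6.3.6 sets its liver criteria in multiples of ULN. Re-testing is triggered by ALT or AST above 3x ULN or AP above 2x ULN. Discontinuation is to be considered above 8x ULN, above 5x ULN lasting more than 2 weeks, and on the combination "ALT or AST > 3 x ULN and (total bilirubin > 2 x ULN or INR > 1.5" (the bracket closes there). Two further items rest on symptoms or eosinophilia, and on a cholestatic pattern with other causes excluded.

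Liver function is one of two laboratory domains singled out in Protocol 10.3.1.4: "Change in liver function measured by bilirubin (total and fractions), AST and ALT from baseline". The SAP repeats this in 6.3.3 and 6.3.6.

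SAP 6.3.6 plans four outputs:

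- "Descriptive analysis of continuous laboratory parameters, and their changes from baseline by visit and treatment group". SAP 4.1 defines the statistics: "mean, standard deviation, minimum, quartiles, median, and maximum will be calculated for metric data".
- "Incidence rates of treatment-emergent laboratory values outside of normal range by treatment group".
- "Listings of laboratory data out of normal range".
- A change-from-baseline table by visit and treatment for eGFR, bilirubin, AST and ALT. AP is not named in it.

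Protocol 10.3.2.4 contains the first three and has no threshold count either.

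On the source of the data, Protocol 9.6.3.1 states "Additional re-tests for liver monitoring (Section 9.6.3.6) will be done locally", and SAP 4.5.3 agrees that liver re-tests are local. SAP 6.3.6 nevertheless states "All laboratory evaluations will be done by central laboratory".

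**The concern.** Drug-induced liver injury shows in the tail: a few patients with large rises, and above all a large aminotransferase rise together with raised bilirubin or INR. A table cut only at the normal range is filled mainly by small excursions, and a mean barely moves when one patient has a large rise. The protocol recognises this, because its own criteria are tail cuts and combinations. The SAP does not carry those cuts into any count by dose.

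This matters because the trial is meant to choose a Phase III dose, and SAP 6.2.1.2 says that the choice also depends on safety. For conduction risk, SAP 6.3.7 plans a count by treatment group of patients with AV block above first degree. The liver has no equivalent.

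**Working it through.** No figure in the documents is in dispute. The check sets the planned outputs against the protocol criteria and then gives one illustration with assumed rates.

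**Step 1. What each planned output can show**

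| Planned output | Shows an extreme value by arm? | Counts patients at a protocol criterion by arm? |
|---|---|---|
| Descriptive statistics by visit (SAP 4.1, 6.3.6) | Yes, through the maximum | No |
| Incidence outside the normal range (6.3.6) | No, all excursions count alike | No |
| Change from baseline in bilirubin, AST, ALT (6.3.6) | Only through a maximum change | No |
| Listing of out-of-range values (6.3.6) | Patient by patient | No |
| Adverse event tables (6.3.4) | If reported as an event | No |
| Adverse events of special interest (6.3.4) | No liver item | No |
| Abnormality tables with unscheduled results (4.5.2) | No cut-off is defined | No |

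No output pairs an aminotransferase with bilirubin or INR in the same patient.

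**Step 2. Role of the re-tests**

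Under Protocol Table 9—1, safety blood is drawn at Weeks 0, 4, 8, 12, 20 and 24, so scheduled samples are 4 to 8 weeks apart. Whether a rise above 5x ULN lasted more than 2 weeks can therefore hardly be judged without the local re-tests.

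**Step 3. Arm sizes (Protocol 7.3 and 10.4)**

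288 patients at 1:2:2:2:2:3 (total 12) gives 24 at 5 mg, 48 at each of 10, 20, 30 and 40 mg, and 72 on placebo.

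**Step 4. Sensitivity of a mean**

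One patient rising from 1x to 8x ULN moves the arm mean by (8 − 1)/48 = 0.15x ULN in an arm of 48, and by 7/24 = 0.29x ULN in the arm of 24.

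**Step 5. Both tables on one scale (rates assumed; the documents give none)**

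The measure is the difference between 40 mg and placebo divided by its standard error (SE), with SE = √(p₁(1 − p₁)/48 + p₀(1 − p₀)/72).

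- Out-of-range table. Assume that 15% in each arm have some new value outside the range, and that an independent 6% at 40 mg exceed 3x ULN because of drug. Then p₁ = 0.15 + 0.06 × 0.85 = 0.201 and p₀ = 0.15. SE = √(0.201 × 0.799/48 + 0.15 × 0.85/72) = 0.0715. Ratio = 0.051/0.0715 = 0.71.
- Row for ALT or AST above 3x ULN. p₁ = 0.06, p₀ = 0.005. SE = √(0.06 × 0.94/48 + 0.005 × 0.995/72) = 0.0353. Ratio = 0.055/0.0353 = 1.56.

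For true rates of 4% to 8% at 40 mg, the threshold row gives 1.2 to 1.9 SE. The out-of-range table gives 0.4 to 1.1 SE over the same rates and backgrounds of 10% to 20%. With so few events the SE is only a common yardstick. As an exact reference, 3 of 48 against 0 of 72 has Fisher p = 0.06.

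**The case against.** The strongest reply is that the SAP offers more than the incidence table and that nothing inferential is harmed. Much of this stands.

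- **Maxima.** SAP 4.1 puts the maximum into the descriptive statistics, so the highest ALT, AST, AP and bilirubin by arm and visit will be seen. A reader might infer that liver tests are summarised only as means; that is not so.
- **Adverse events.** Protocol 9.6.1.1 counts abnormal laboratory findings as possible adverse events. SAP 6.3.4 tabulates these by arm, including those leading to withdrawal or interruption, and an unblinded DMC reviews safety. A reader might infer that a dose-related cluster would appear in no table by arm. That goes too far, although these tables depend on investigators reporting an event.
- **Unscheduled values.** SAP 4.5.2 and 4.5.3 already bring them into tables. What remains open is whether local re-tests count as unscheduled data, given the central-laboratory sentence in 6.3.6.
- **Treatment-emergent.** One could read this as requiring a normal baseline, so that a patient entering above ULN could never be counted. The SAP does not define the term for laboratory values, and its adverse event definition covers worsening as well as onset. The restrictive reading is speculation.
- **Standing.** The SAP follows Protocol 10.3.2.4, safety is descriptive, table shells are not among the documents, and the documents single out no hepatic signal.

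What survives is narrow: none of these outputs counts patients by liver threshold and dose. SAP Section 1 says that the SAP describes the study tables, so the omission cannot simply be left to shells.

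**Conclusion.** The point holds in limited form. SAP 6.3.6 specifies no count by treatment group at the Protocol 9.6.3.6 criteria, its single categorical cut does not separate mild from marked elevations, and no joint assessment with bilirubin or INR is planned.

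The gain from a threshold row is real but moderate: about 1.6 against 0.7 SE at the assumed rates. It should not be read as a powered comparison. Under the same 6% against 0.5%, a one-sided Fisher test at 5% would have power of about 27%. The value of the table is that it lets the doses be compared on the protocol's own scale. The illustration rests on assumed event rates and on planned arm sizes; the finding about the missing table needs neither.

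No primary or secondary efficacy analysis is affected. This is an inexpensive improvement that should be made before the data are unblinded.

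**What to change.** Add to SAP 6.3.6 a table by treatment group on the safety analysis set, covering any time after first dose up to 6 weeks after last dose and irrespective of baseline. Count patients with:

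- ALT or AST > 3x ULN
- ALT or AST > 5x ULN for more than 2 weeks
- ALT or AST > 8x ULN
- AP > 2x ULN
- ALT or AST > 3x ULN with total bilirubin > 2x ULN or INR > 1.5

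Add a listing of the patients in the last row, and say how values are paired in time for it. Any value > 5x ULN and bilirubin > 2x ULN alone may be shown as descriptive rows, labelled as not being protocol criteria. The symptom-based and cholestasis items need information beyond these values, so the table title should say that it covers laboratory criteria only.

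State in SAP 4.5.3 and 6.3.6 that local liver re-tests count as unscheduled data and are divided by their own laboratory's ULN, and reconcile this with the central-laboratory sentence.

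The cost is SAP wording, one table and one listing, mostly from data already collected. The downside is that local values and reference ranges must be in the database. The table counts patients at existing criteria and changes no rule for monitoring or stopping treatment.
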